#### **Section 7.2.1.2 of the CTP:**

*Serum concentration data and parameters of a patient will be included in the PK analyses if they are not flagged for exclusion due to a protocol deviation relevant to the evaluation of PK (to be decided no later than in the Report Planning Meeting) or due to PK non-evaluability (as revealed during data analysis, based on the criteria specified below). Exclusion of a patient's data will be documented in the CTR.*

*Relevant protocol deviations may be*

- *Incorrect trial medication taken, i.e. the patient received at least one dose of trial medication the patient was not assigned to*
- *Incorrect dose of trial medication taken*
- *Use of restricted medications*

*Serum concentrations and/or PK parameters of a patient will be considered as non-evaluable, if for example there were missing samples/concentration data at important phases of PK disposition curve.*

*Serum concentration data and PK parameters of a patient which is flagged for exclusion will be reported with its individual values but will not be included in the statistical analyses. Only concentration values within the validated concentration range and actual sampling times will be used for the calculation of pharmacokinetic parameters. Concentrations used in the pharmacokinetic calculations will be in the same format as in the bioanalytical report (that is to the same number of decimal places provided in the bioanalytical report).*

The descriptive analysis of PK concentrations will be based on the ADS ADPC as described in [Section 7](#).

Table 6.3: 1 Subject sets analysed

Class of endpoint	ES	TS	PKS
Primary endpoints and further safety assessments (incl. ECG)		X	
Analysis of biomarker		X	
Analysis of PK endpoints (secondary and further)			X
ADA analysis		X	
Demographic/baseline parameters		X	
Important protocol deviations		X	
Disposition	X		
Exposure		X	

## 6.5 POOLING OF CENTRES

Due to the limited number of patients, all patients will be pooled without using different weights for centres.

## 6.6 HANDLING OF MISSING DATA AND OUTLIERS

Handling of missing data and outliers will be performed as described in the CTP, Section 7.3.

The only exceptions where imputation might be necessary for safety evaluation are AE dates. Missing or incomplete AE dates are imputed according to BI standards (see BI-KMED-BDS-HTG-0035 ([4](#))).

Missing data and outliers of PK data are handled according to BI standards (see BI-KMED-TMCP-MAN-0014 ([5](#))).

Missing baseline laboratory values will be imputed by the respective values from screening.

If single cardiac cycles of an ECG (out of the generally four) are missing, the arithmetic mean for this single ECG will be computed with the reduced (1, 2 or 3) number of cardiac cycles.

If replicate ECG recordings are missing, the arithmetic means per time point will be computed with the reduced number (1 or 2) of recordings.

For the classification of the on treatment QTc/QT intervals into ‘no new onset’ / ‘new onset’ categories, the handling of missing value is described in Appendix [Section 10.1.2](#).

## 6.7 BASELINE, TIME WINDOWS AND CALCULATED VISITS

The baseline value for laboratory data, vital signs data and ophthalmological data is defined as the last measurement before first administration of BI 754132 (= value at V2, in case no actual time is given in data).

**Section 5.2.4 of the CTP:** *For the endpoints, baseline is defined as the value at Visit 2; if not measured at Visit 2 then baseline is the value at Visit 1.*

The acceptable time windows for visits are given in the CTP Flow Charts.

Adherence to time windows will be checked via the consistency check listings at the RPM/DBLM.

Unscheduled measurements of laboratory data, ophthalmologic data and vital signs data will be assumed to be repeat measurements of the most recent scheduled measurement (e.g. for follow-up or confirmation of a particular value). Therefore, unscheduled measurements will be assigned to the planned time point of the previous scheduled measurement.

**Section 5.2.6 of the CTP:** *Central ECG lab evaluation will be performed for all ECGs indicated in the CTP Flow Charts. For all ECGs, this will include the intervals RR, PR, QRS and QT measured semi-automatically. The screening ECGs will be checked for abnormalities. [...].*

At Visit 1, single ECGs will be recorded. At Visit 2-10, triple ECGs will be recorded (three single ECGs within 180 sec).

**Section 7.2.5 of the CTP:** *The baseline value of an ECG variable is defined as the mean of the ECG measurements prior to drug administration on visit 2. The screening ECGs will not be included in calculation of baseline.*

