### 7.2.5 Safety analyses

Adverse events will be coded using the Medical Dictionary for Drug Regulatory Activities (MedDRA). Standard BI summary tables and listings will be produced. For BI 754132, the residual effect period (REP) after IVT administration is not known. Therefore, all AEs with

an onset between start of treatment and the respective EOT visit will be assigned to the on-treatment period for evaluation. The safety analysis will be performed by planned dose group.

All treated patients will be included in the safety analysis. In general, safety analyses will be descriptive in nature and will be based on BI standards. No hypothesis testing is planned.

Statistical analysis and reporting of adverse events will concentrate on treatment-emergent adverse events, i.e. all adverse events occurring between start of treatment and the EOT visit. Adverse events that start before first drug intake and deteriorate under treatment will also be considered as ‘treatment-emergent’.

Frequency, severity, and causal relationship of adverse events will be tabulated by system organ class and preferred term after coding according to the current version of the Medical Dictionary for Drug Regulatory Activities (MedDRA) at database lock.

Laboratory data will be analysed both quantitatively as well as qualitatively. The latter will be done via comparison of laboratory data to their reference ranges. Values outside the reference range as well as values defined as clinically relevant will be summarised. Treatment groups will be compared descriptively with regard to distribution parameters as well as with regard to frequency and percentage of patients with abnormal values or clinically relevant abnormal values.

Vital signs, physical examinations, or other safety-relevant data observed at screening, baseline, during the course of the trial and at the end-of-trial evaluation will be assessed with regard to possible changes compared to findings before start of treatment.

A centralised evaluation of all 12-lead ECGs recordings (see [Section 5.2.6](#)) will be the basis for the ECG variables QT, HR, QTcF, PR, QRS, RR, and further derived ECG endpoints. The baseline value of an ECG variable is defined as the mean of the ECG measurements prior to drug administration. The derivation of the quantitative and qualitative ECG endpoints and their analyses will be described in the TSAP.

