#### **CTP Section 7.2.5:**

*For BI 754132, the residual effect period (REP) after IVT administration is not known. Therefore, all AEs with an onset between start of treatment and the respective EOT visit will be assigned to the on treatment period for evaluation.*

The following separate study phases will be defined for the analyses of AEs:

- **Screening** (ranging from 0:00h (midnight) on day of informed consent until first administration time of BI 754132)
- **On treatment**
  - **BI treatment** (separately for each treatment, ranging from the time of first administration of BI 754132 until 0:00h (midnight) on the day after trial completion date)

Please note that all AEs reported between start of trial drug administration and the last per-protocol contact will be considered on treatment (i.e. no follow-up period is considered in this trial).

The following AE displays will be provided in the report:

Section 15.3 and Appendix 16.1.13.1.8 (for ClinicalTrials.gov and EudraCT) of the CTR displays:

In these displays, the on treatment phase will be analysed (labelled with the short label of the study treatment). Screening will not be included in this analysis.

The following totals will be provided in addition in Section 15.3:

- a total over all on treatment phases included in this analysis ("Total") (SRD part only)

In Section 15.4 and Appendix 16.2 (Listings) of the CTR displays, the screening period will be included and no totals will be provided.

For detailed information on the handling of the treatments refer to Technical TSAP ADS (analysis data set) plan and Analysis Data Reviewers guide.

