### **7.8.2      Laboratory data**

The analyses of laboratory data will be descriptive in nature and will be based on BI standards [BI-KMED-BDS-HTG-0042] ([10](#)).

Laboratory data will be analysed qualitatively via comparison of laboratory data to their reference ranges. Values outside the reference range as well as values defined as possibly clinically significant will be flagged in the data listings.

Clinically relevant findings in laboratory data will be reported as baseline conditions (at screening) or as adverse events (during the trial) if judged clinically relevant by the investigator, and will be analysed as such.

It is the investigator's responsibility to decide whether a lab value is clinically significantly abnormal or not (at the RPM/DBLM at the latest).

Descriptive statistics of laboratory data (normalised values) including change from baseline will be calculated by time point based on the worst value of the patient at that time point (or assigned to that planned time point).

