### **7.8.3      Vital signs**

For vital signs (blood pressure, pulse rate and body weight), descriptive statistics including change from baseline will be calculated by treatment group and by planned time point based on the first value of the patient at that planned time point (or assigned to that planned time point). In the listing the difference from baseline will also be displayed.

Clinically relevant findings in vital signs will be reported as AEs.

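### SAP 6.7 does not stop at the first injection, so an unscheduled on-drug laboratory value can enter the pre-dose Visit 2 row

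*SAP*

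**What the plan says.** SAP 6.7 treats unscheduled laboratory, ophthalmologic and vital-signs values as repeats of the latest scheduled one, for example to confirm a result. It concludes that "unscheduled measurements will be assigned to the planned time point of the previous scheduled measurement". Nothing in that section separates values before the first dose from values after it.

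The same section defines baseline separately, as the "last measurement before first administration of BI 754132 (= value at V2, in case no actual time is given in data".

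The summary statistics differ by data type:
- Laboratory (SAP 7.8.2): descriptive statistics and change from baseline by time point, "based on the worst value of the patient at that time point (or assigned to that planned time point".
- Vital signs (SAP 7.8.3): the same kind of table, but "based on the first value of the patient at that planned time point" or assigned to it.

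For adverse events the SAP does divide time at the first dose. In SAP 6.1 the screening phase runs from midnight "on day of informed consent until first administration time of BI 754132", and everything after that is on treatment.

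Protocol 6.2.1.3 and 6.2.2.3 let the investigator arrange unscheduled visits at any time for safety. Protocol 5.2.8.1.4 calls for an unscheduled blood test, if needed, when symptoms suggest hepatic injury and no liver values are available.

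**The concern.** Treating an extra value as a repeat is sensible when both values come from the same side of the first injection. It fails when the scheduled value was taken before the drug and the extra value after it, because the second is then new information about exposure and not a confirmation of the first.

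The Visit 2 row of a laboratory table is read as the patients' state before treatment. If it can hold on-drug values, the reader is misled in two ways: the pre-dose row looks worse than it was, and the on-treatment rows omit the value. An extra safety sample is also likely to be taken because something prompted it.

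Protocol 7.2.5 says that vital signs, physical examinations and other safety data "will be assessed with regard to possible changes compared to findings before start of treatment". Protocol 1.2 (Toxicology) names haematology, with body weight, heart rate and blood pressure, among the potential systemic effects to monitor.

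**Working it through.** **Inputs**
- MD part (Flow Chart II, Tables 4.1.4:2 and 10.3:2): first injection at Visit 2, Day 1; Visit 3 on Day 29 ± 3.
- SRD part (Flow Chart I): injection at Visit 2, Day 1; Visit 3 on Day 4 ± 1.
- Laboratory tests are scheduled at Visits 2 and 3 in both parts.

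**Reproducing the plan's own figure.** (29 − 1) days × 24 h = 672 h, the planned time of the second administration in Table 10.3:2 (672:00).

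**Interval in which the rule crosses the first injection**
- MD: 29 − 1 = 28 days. With the window: 26 − 1 = 25 to 32 − 1 = 31 days.
- SRD: 4 − 1 = 3 days. With the window: 3 − 1 = 2 to 5 − 1 = 4 days.

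From Visit 3 on, the rule moves a value back to a visit that is itself after the first dose, so the boundary is no longer crossed.

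**Following one value through the rules.** Let x be a patient's scheduled pre-dose Visit 2 value and y an unscheduled value taken in the interval.

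| Step | Laboratory | Vital signs |
|---|---|---|
| Time point assigned (SAP 6.7) | Visit 2 | Visit 2 |
| Value used in Visit 2 row | the worse of x and y (7.8.2) | x, the first value (7.8.3) |
| Baseline (SAP 6.7) | x | x |
| Change from baseline in Visit 2 row | y − x if y is worse, otherwise 0 | 0 |
| Does y appear in a post-dose row? | no | no |

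For laboratory data, a worse y therefore produces a non-zero change from baseline at the visit that supplies the baseline. If all 6 planned MD patients have a Visit 2 value and one has such a y, the Visit 2 mean moves by (y − x)/6. In an SRD cohort of 3 it moves by (y − x)/3. The documents give neither the size of y − x nor how often such a y would occur, so this cannot be turned into an effect size.

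For vital signs the Visit 2 row is unchanged as long as the scheduled value exists; y simply does not enter the by-visit table.

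**Later rows.** Change from baseline at Visit 3 onward uses x as baseline and the values belonging to those visits. It is not altered.

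**The case against.** The strongest case against is that little of consequence depends on the rule.

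- **Baseline is protected by its own definition.** A reader might infer that baseline is contaminated. The documents do not support that: baseline must precede first administration, and the Visit 2 fallback applies only where no actual time is recorded. A value dated on a later day is recognisably not baseline. This stands.
- **Vital signs give no wrong number.** A reader might expect the Visit 2 vital-signs statistics to be distorted as well. The first-value rule prevents that. This stands; for these data the issue is omission only.
- **Absence from post-dose rows is not a measure of harm.** An off-schedule value belongs to no scheduled row unless visits are windowed, and every scheduled row keeps its own data. This stands. The real defect is the value's possible presence in the pre-dose row.
- **Signals are captured elsewhere.** Clinically relevant findings become adverse events, which are phased by administration time. Individual values are listed, and out-of-range laboratory values "will be flagged in the data listings". With 6 MD patients, listings are a practical way to read a stray value. This limits the consequence but does not correct the table row.
- **Unseen documents may settle it.** SAP 7.8.2 relies on a sponsor laboratory standard, and SAP 6.1 points to an analysis-dataset plan for handling treatments. Either may contain a pre-dose restriction. This is possible, but the visible rule is explicit and carries no such exception.

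**Conclusion.** The point holds as a minor one, essentially for laboratory tables. As written, SAP 6.7 and 7.8.2 allow an on-drug laboratory value from the 28 days (25 to 31) after the first MD injection, or the 3 days (2 to 4) after the SRD injection, to stand as that patient's Visit 2 entry. This is a stated rule giving a wrong table row, not merely missing detail.

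It rests on three assumptions:
- The scheduled Visit 2 safety laboratory sample is taken before the injection. The documents do not say so outright; the baseline definition and the replacement of missing baseline laboratory values by screening values imply it.
- At least one unscheduled laboratory value falls in the interval and is worse than the scheduled one.
- No cited standard or dataset plan overrides the visible text.

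The analysis of the primary endpoints does not use these by-visit tables. Which intraocular pressure reading is summarised at a visit, and whether out-of-range laboratory values are to be summarised (protocol 7.2.5) or only flagged (SAP 7.8.2), are separate questions and form no part of this conclusion.

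**What to change.** 1. In SAP 6.7, state that an unscheduled value taken after first administration is not assigned to a time point before first administration (Visit 1 or pre-dose Visit 2), but is kept as an unscheduled on-treatment record. Visit 1 and Visit 2 rows then use pre-dose values only. Repeats on the same side of the first dose stay with the visit they repeat.
2. In SAP 7.8.2, add a worst on-treatment value row that includes unscheduled values, and state for each parameter which direction counts as worst. Without this row, step 1 would take the value out of the pre-dose row but leave it in no summary. The same row could optionally be added to the vital-signs table in SAP 7.8.3.

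The cost is a few lines of SAP text and one extra row per table; no new data are needed. If the cited laboratory standard or the analysis-dataset plan already restricts Visit 1 and Visit 2 rows to pre-dose values and handles these records, a cross-reference in SAP 6.7 is enough.

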## **7. PLANNED ANALYSIS**

Results will be shown separately for SRD part and MD part (except some outputs in Appendix 16.1.13.1).

Safety analysis (refer to [Section 7.8](#)) will be performed by [REDACTED] and will be presented in Sections 15.1 to 15.4 of the CTR and in Appendix 16.2 and 16.1.13.1.

The prior specified in the CTP, Section 7.2.1.1 will be used in all BLRM evaluations.

Descriptive data analysis of PK parameters and concentrations will be performed by the [REDACTED] and will be presented in Section 15.6 and in Appendix 16.1.13.5 of the CTR.

[REDACTED]

The format of the listings and tables will follow the BI standards (see BI-KMED-BDS-HTG-0045 ([6](#)) with the exception of those generated for PK-calculations following BI standards for PK/PD analysis ([7](#)).

The individual values of all patients will be listed, sorted by treatment group, patient number, and visit.

The listings will be included in Appendix 16.2 of the CTR.

For end-of-text tables, the set of summary statistics for non-PK parameters is:

N	number non-missing observations
Mean	arithmetic mean
SD	standard deviation
Min	minimum
Median	median
Max	maximum

For analyte concentrations and PK parameters, the following descriptive statistics will additionally be calculated:

Nobs	number of observations
CV	arithmetic coefficient of variation
gMean	geometric mean
gCV	geometric coefficient of variation
P10	10th percentile
Q1	1st quartile
Q3	3rd quartile
P90	90th percentile

The data format for descriptive statistics of concentrations will be identical with the data format of the respective concentrations. The descriptive statistics of PK parameters will be

calculated using the individual values with the number of decimal places as provided by the evaluation program. Then the individual values as well as the descriptive statistics will be reported with three significant digits in the CTR.

Tabulations of frequencies for categorical data will include all possible categories available in the eCRF and will display the number of observations in a category, as well as the percentage (%) for each treatment group. Percentages will be rounded to one decimal place and will be based on all patients in the respective subject set whether they have non-missing values or not. The category 'missing' will be displayed only if there are actually missing values.

#### Exclusion of PK parameters

The ADS ADPP (PK parameters) contains column variables APEX and APEXCO indicating inclusion/exclusion (APEX) of a PK parameter and an analysis flag comment (APEXCO). All analyses based on the PKS will include parameters only if they are not flagged for exclusion, that is APEX is equal to "Included".

#### Exclusion of PK concentrations

The ADS ADPC (PK concentrations per time-point or per time-interval) contains column variables ACEX or ACEXCO indicating inclusion/exclusion (ACEX) of a concentration and an analysis flag comment (ACEXCO). Exclusion of a concentration depends on the analysis flag comment ACEXCO. For example, if ACEXCO is set to 'ALL CALC', the value will be excluded for all types of analyses based on concentrations. If ACEXCO is set to 'DESC STATS', the value will be excluded from descriptive evaluations per planned time point/time interval. If ACEXCO contains the addition 'TIME VIOLATION' or 'TIME DEVIATION', the value can be used for further analyses based on actual times. If ACEXCO is set to 'HALF LIFE', the value will be excluded from half-life calculation (and, as a consequence, any calculation that relies on  $\lambda_z$ ) only; the value is included for all other analyses.

Further details are given in BI-KMED-TMCP-MAN-0014 "Noncompartmental Pharmacokinetic / Pharmacodynamic Analyses of Clinical Studies" (5) and BI-KMED-TMCP- MAN-0010: "Description of Analytical Transfer Files and PK/PD Data Files" (11).

## 7.1 DEMOGRAPHIC AND OTHER BASELINE CHARACTERISTICS

Only descriptive statistics are planned for this section of the report, based on the TS.

The data will be summarised by treatment group (SRD and MD part) and in total (SRD part only).

## 7.2 CONCOMITANT DISEASES AND MEDICATION

Frequency tables are planned for this section of the report, based on the TS.

Concomitant diseases will be coded using the latest version of the coding system of the Medical Dictionary for Drug Regulatory Activities (MedDRA). Medications will be coded using the latest version of the World Health Organization Drug Dictionary (WHO-DD). The coding version number will be specified during RPM. The coding version number will be displayed as a footnote in the respective output.

The diagnoses and medications will be listed. Patients without any concomitant diagnoses or concomitant therapies should be marked with a “No” in the respective column.

The relevance of the concomitant therapies to the evaluation of PK will be decided no later than at the RPM/DBLM.

## 7.3 TREATMENT COMPLIANCE

**Section 4.3 of the CTP:** *Compliance will be assured by administration of all trial medication in the study centre under supervision of the investigating physician or a designee. The measured sample concentrations will provide additional confirmation of compliance.*

It is not intended to list the compliance separately. Any deviations from complete intake will be addressed in the RPM/DBLM (see [Section 6.2](#)) and described in the CTR.

## 7.4 PRIMARY ENDPOINTS

### SRD part:

**Section 5.2.1 of the CTP:** *A dose limiting event (DLE) is defined as the occurrence of any of the following events as ocular DLE (in the study eye):*

- *Development of sterile endophthalmitis and/or sterile inflammation of the vitreous grade 3+ according to Standardization of Uveitis Nomenclature (SUN) working group (WG) grading scheme for anterior chamber cells measured by slit lamp and a duration of 5 or more days*
- *Visual loss of more than 15 letters at any given time point due to treatment effect in the study eye confirmed on consecutive visits*
- *Persistent IOP over 30 mmHg for 3 days*
- *Signs of vascular occlusion in the retina (haemorrhage of the macula would not be included as this is a possible sign of CNV occurrence; peripheral retinal haemorrhage may be a sign of vascular occlusion)*

[...]

or as systemic DLE:

- *Drug-related AEs of moderate and severe intensity according to CTCAE (14) out of the following:*
  - *Self-reporting paraesthesia, dysgeusia, taste abnormality, taste disorder, hyposmia (15)*
  - *Diarrhea, cough (16)*

*Each DLE needs to be reported as AESI.*

Descriptive statistics (number and percentage of patients with ocular (in study eye) and systemic DLEs) will be provided by treatment group and in total, based on the TS.

The results of the final BLRM after completion of the SRD part will be provided based on the TS, and based on the DLE evaluable set in case the DLE evaluable set and the TS differ.

